2.7.4 Other safety data

2.7.4.1 ECG and cardiac imaging data

The following quantitative variables will be summarized: heart rate and QRS duration. Summary statistics for continuous data and number and percentage of participants for categorical data (e.g. interpretation) will be provided by treatment and visit for randomization period.

In addition, shift tables comparing the existence or not of abnormalities (atrial fibrillation, atrial flutter, LBB block, RBB block, left ventricular hypertrophy, paced rhythm, myocardial infarction, 1st degree AV block, 2nd degree AV block, 3rd degree AV block or other) on the ECG at baseline and worst-on study results (during the randomized treatment period and during the randomization period) will be provided. The categories Yes, No and Missing will be used to reflect where the abnormality of interest is present, absent or an ECG was not performed/is not available, respectively for that participant, where "Yes" is defined as any one of the abnormality interpretation is checked, "No" is defined as ECG evaluation is performed and none of the abnormality interpretation is reported and "Missing" if ECG evaluation is not performed at the visit.

The analysis will be based on SAF.

2.7.4.2 Vital signs

Vital signs including weight, blood pressure and pulse measures will be summarized by treatment group and scheduled visit with standard summary statistics (mean, Q1, median, Q3, standard deviation, min, max), including changes from randomization baseline. Graphical mean plots with 95% CIs for these vital signs will also be provided. Change from baseline will only be summarized for participants with both baseline and post-baseline values and will be calculated as:

[figure not shown]
• change from baseline = post-baseline value – baseline value

The number and percentage of participants with clinically notable vital signs after baseline will be presented in accordance with Table 2-4 for randomized treatment period and randomization period, by visit and overall. The analysis will be based on SAF.

Apart from the above analyses, values for vital signs parameters will also be listed at a participant level by treatment group and visit for all participants in safety set (SAF).

Maximum and minimum of 24 hour blood pressure and heart rate values will be summarized by visit (mean, Q1, median, Q3, standard deviation, min, max) for randomized treatment period and for randomization period.

[figure not shown]

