5.1 Inclusion criteria

Participants eligible for inclusion in this study must meet **all** of the following criteria:

- 1. Male and female participants who are \geq 18 years old.
- 2. Signed informed consent prior to participation in the study.
- 3. Apparent rHTN at screening (Visit 1) defined as uncontrolled BP with an office msSBP ≥ 140 mmHg despite treatment with stable (i.e., unchanged for ≥4 weeks), optimal or maximally tolerated doses of three or four antihypertensive drugs of different classes, including an ACEI/ARB, a long-acting dihydropyridine CCB, and a thiazide or thiazide-like diuretic. Participant with documented intolerance to any doses of CCBs may be eligible if receiving another class of antihypertensive medication at an optimal or maximally tolerated dose (referred to as triple background antihypertensive therapy. An optimal dose is defined as the highest dose taking in to account participant's documented comorbidities and tolerability per investigator's clinical judgment. Refer to Section 10.8 for recommended minimum doses of some commonly prescribed ACEI/ARBs, long acting dihydropyridine calcium channel blockers and thiazide diuretics.
- 4. Mean 24hr SBP ≥135 mmHg (measured by ABPM) at the end-of Run-in-Visit (Visit 30) on treatment with optimal or maximally tolerated doses of an ACEI/ARB, a long-acting dihydropyridine CCB (or a suitable alternative in case of intolerance per inclusion criterion above), and a thiazide or thiazide-like diuretic.

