Plasma glucose	> 25% increase
	value < 40 mg/dL
Blood pressure increase (mean mean mean mean mean mean mean mean	
Mean sitting office SBP (mmHg)	> 180 mmHg
Mean sitting office DBP (mmHg)	> 110 mmHg
Blood pressure decrease (mean m	neasurement)
1. Mean sitting office SBP (mmHg)	< 110 mmHg
2. Mean sitting office DBP (mmHg)	< 70 mmHg
3. Criteria 1 OR 2	Participants meeting either criterion 1 OR criterion 2
4. ABPM day time mean SBP (mmHg)	< 110 mmHg
5. ABPM day time mean DBP (mmHg)	< 70 mmHg
6. Criteria 4 OR 5	Participants meeting either criterion 4 OR criterion 5
7. ABPM night time mean SBP (mmHg)	< 90 mmHg
8. ABPM night time mean DBP (mmHg)	< 55 mmHg
9. Criteria 7 OR 8	Participants meeting either criterion 7 OR criterion 8
10. ABPM mean 24 hours SBP (mmHg)	< 105 mmHg
11. ABPM mean 24 hours DBP (mmHg)	< 65 mmHg
12. Criteria 10 OR 11	Participants meeting either criterion 10 OR criterion 11
13. Any one criteria	Participants meeting any one of the criteria 1 to 12
He aut mate't in anne :	
Heart rate* increase	. 400
Pulse (bpm)	> 100
Heart rate* decrease	
Pulse (bpm)	1. < 60
	0

2. < 50

Orthostatic hypotension

Parameter	Clinical notable criteria
Systolic blood pressure (mm Hg) minute after standing	≥ 20 mmHg reduction from corresponding mean measurement in sitting position
Diastolic blood pressure (mm Hg) minute after standing	≥ 10 mmHg reduction from corresponding mean measurement in sitting position
3. Systolic blood pressure (mm Hg) 3 minutes after standing	≥ 20 mmHg reduction from corresponding mean measurement in sitting position
4. Diastolic blood pressure (mm Hg) 3 minutes after standing	≥10 mmHg reduction from corresponding mean measurement in sitting position
5. Criteria 1 OR 2	Participants meeting either criterion 1 OR criterion 2
6. Criteria 3 OR 4	Participants meeting either criterion 3 OR criterion 4
7. Criteria 5 OR 6	Participants meeting either criterion 5 OR criterion 6
Liver function tests	
ALT (SGPT) OR AST (SGOT)	1. value > 3 x ULN
	2. value > 5 x ULN
	3. value > 8 x ULN
	4. value > 10 x ULN
	5. value > 20 x ULN
ALT (SGPT) OR AST (SGOT) AND	1. ALT or AST > 3 x ULN and TB > 1.5 x ULN
Total bilirubin (TB)	2. ALT or AST > 3 x ULN and TB > 2 x ULN
	3. ALT or AST > 5 x ULN and TB > 2 x ULN
	4. ALT or AST > 8 x ULN and TB > 2 x ULN
	5. ALT or AST > 10 x ULN and TB > 2 x ULN
	6. ALT or AST > 20 x ULN and TB > 2 x ULN
Alkaline phosphatase	1. > 2 x ULN
	2. > 3 x ULN
	3. > 5 x ULN
Total bilirubin	1. > 1.5 x ULN
	2. > 2 x ULN

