AH 15 1 1 1 (ALE) AND	3. > 3 x ULN
Alkaline phosphatase (ALP) AND TB	1. ALP > 3 x ULN AND TB > 2 x ULN
	2. ALP > 5 x ULN AND TB > 2 x ULN
ALT (SGPT) OR AST (SGOT) AND Total bilirubin (TB) AND Alkaline	1. ALT OR AST > 3 x ULN AND TB > 2 x ULN AND ALP ≤ 2 x ULN
phosphatase (ALP)	2. ALT OR AST > 3 x ULN AND TB > 2 x ULN AND ALP ≤ 2 x ULN OR reported H"s Law case
	3. TB > 3 x ULN AND AST OR ALT \leq 3 x ULN AND ALP \leq 1.5 x ULN
	4. ALP > 3 x ULN AND AST AND ALT AND TB are within normal range
Laboratorial and clinical associations	ALT OR AST > 3 x ULN AND (Nausea OR Vomiting OR Fatigue OR General malaise OR Abdominal pain OR (Rash AND Eosinophilia))

Parameter	Clinical notable criteria
Renal function tests	
eGFR	1. > 25% decrease
	2. > 40% decrease
	3. > 50% decrease
	4. > 30 mL/min/1.73m ² decrease
	5. Participants meeting any of the criteria 1 to 4 above
Creatinine	1. ≥ 0.3 mg/dL increase
	2. ≥1.5 to ≤ 1.9 x baseline
	3. >1.9 to ≤ 2.9 x baseline
	4. > 2.9 x baseline
	5. ≥ 4.0 mg/dL
	6. Participants meeting either criterion 1 OR 2 above
	7. Participants meeting either criterion 4 OR 5 above
New onset of proteinuria	Urine protein ≥ 300 mg/dL
New onset of hematuria	Urine hemoglobin ≥ 1 mg/dL

ULN: upper limit of the normal range; LLN: lower limit of the normal range; SBP: systolic blood pressure; DBP: diastolic blood pressure; ABPM: ambulatory blood pressure measurement; Increases and decreases of parameters as mentioned in the table are from baseline; * Heart Rate: increase or decrease is based on 24hr mean measurement of ABPM.

Participants with liver function tests (ALT, AST, ALP, Total Bilirubin) and renal-related parameters falling within predefined categories of elevations (new and worsened [i.e. those existent before, and that worsened after randomization] elevations) will be summarized by treatment group in accordance with Table 2-4 for both run-in period, randomized treatment period and randomization period. Descriptive summaries by presenting count and percentage of participants with each type of Liver and Renal event in addition to graphical summaries will be displayed, as applicable.

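### The diastolic and orthostatic rows of SAP Table 2-4, and the composites built on them, do not separate findings already present at baseline from those arising on treatment

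*SAP*

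**What the plan says.** SAP 2.7.4.2 sets the counting rule for vital signs: "The number and percentage of participants with clinically notable vital signs after baseline will be presented in accordance with Table 2-4". The counts are given by visit and overall, for the randomized treatment period and for the longer randomization period. The words about baseline fix when a value is measured. They say nothing about whether the participant already met the criterion.

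Table 2-4 (SAP 2.7.3) defines the criteria:

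- **Diastolic decrease rows (2, 5, 8, 11):** office below 70, daytime below 70, night below 55, 24-hour below 65 mmHg.
- **Systolic decrease rows (1, 4, 7, 10):** office below 110, daytime below 110, night below 90, 24-hour below 105 mmHg.
- **Composites (3, 6, 9, 12):** either the systolic or the diastolic row. Criterion 13 is "Participants meeting any one of the criteria 1 to 12".
- **Orthostatic rows (1–4):** at 1 and 3 minutes after standing, a systolic "≥ 20 mmHg reduction from corresponding mean measurement in sitting position", or a diastolic reduction of at least 10 mmHg. Rows 5–7 combine them.

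The table footnote adds: "Increases and decreases of parameters as mentioned in the table are from baseline".

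For liver and renal parameters, SAP 2.7.3 counts "new and worsened [i.e. those existent before, and that worsened after randomization] elevations". In the same table proteinuria and hematuria are defined as new onset, and the first set of ALT, AST, alkaline phosphatase and bilirubin criteria depends on whether baseline was normal.

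At entry, Protocol 5.1 requires "Mean 24hr SBP ≥135 mmHg (measured by ABPM) at the end-of Run-in-Visit (Visit 30". Protocol 5.2 excludes office systolic pressure below 140 mmHg at Visit 20. For diastolic pressure it sets upper limits only (office 110 or more, 24-hour above 105). Orthostatic hypotension is not among the exclusions.

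**The concern.** Hypotension is the reason the highest dose is introduced in a staggered way (Protocol 2.3). It is an adverse event of special interest when serious (Protocol 8.6.6) and a listed potential risk in any form (SAP 2.7.1.1). Among the planned displays, Table 2-4 is the one that gives rates of measured threshold crossings by arm.

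A participant with systolic hypertension and a diastolic pressure of 66 mmHg at baseline can be enrolled. If the pressure does not change on placebo, that participant is counted as a notable decrease. The same holds for someone whose pressure already drops on standing at baseline. Under randomization such cases are expected equally in all arms, so they raise the background rate everywhere and shrink the relative difference between a dose and placebo. For a safety display that is the unfavourable direction, because it can obscure separation between doses at 34 participants per arm.

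**Working it through.** The plan states no figure on this point, so there is nothing to reproduce. The main check sets the cut-offs against the entry criteria. The arithmetic after that is illustrative and rests on assumed distributions.

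**1. Which rows can be met at baseline**

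- 24-hour systolic: the entry floor is 135 and the cut-off is below 105. An eligible participant must fall by more than 135 − 105 = 30 mmHg to be counted, so the row cannot be met at the qualifying recording.
- Office systolic: the floor of 140 at Visit 20 is 140 − 110 = 30 mmHg above the cut-off. There is no office floor at Visit 30, but a baseline value below 110 is very unlikely in someone whose 24-hour mean is at least 135. The daytime and night systolic rows are very unlikely for the same reason.
- All four diastolic rows: no entry floor, so they can be met.
- Orthostatic rows: no exclusion, so they can be met.
- Composites: each BP composite contains a diastolic row and each orthostatic composite contains orthostatic rows, so all inherit the problem.

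**2. Whether the footnote resolves it.** A requirement that the value be lower than baseline would still count 67 mmHg after a baseline of 68. For the orthostatic rows the comparison is with sitting pressure at the same visit, so a decrease from baseline has no defined meaning there.

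**3. Possible size for office diastolic pressure below 70.** Assumptions: normal distribution, mean μ of 78–90 mmHg, between-person and within-person SDs of 9 and 5 or 10 and 6, no drug effect. Office visits after baseline are at Weeks 2, 4, 8, 9 and 12 on treatment (5), plus Weeks 16 and 20 in follow-up (7 in all).

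Share below 70 at baseline = Φ((70 − μ)/√(SD_between² + SD_within²)):

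- μ = 78, SDs 10/6: Φ(−8/11.66) = 24.6%
- μ = 82, SDs 10/6: Φ(−12/11.66) = 15.2%; SDs 9/5: Φ(−12/10.30) = 12.2%. That is about 4–5 of 34.
- μ = 90, SDs 9/5: Φ(−20/10.30) = 2.6%

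Simulation of 400,000 participants at μ = 82 (the range is over the two SD pairs):

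| | 5 visits | 7 visits |
|---|---|---|
| Flagged at any visit | 26–32% | 29–36% |
| Share of flagged already below 70 at baseline | 40–41% | 38% |
| Flagged among baseline-negative participants | 17–22% | 21–26% |

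Across means of 78–90, both SD pairs and both visit counts, 7–50% are flagged, of whom about 25–48% were already below 70 at baseline.

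**4. Possible size for 24-hour diastolic pressure below 65.** SDs 9/5, two post-baseline recordings, no drug effect:

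| Assumed mean (mmHg) | Flagged | Of flagged, already below 65 at baseline | New onset, as share of all |
|---|---|---|---|
| 75 | 23% | 52% | 11% |
| 80 | 11% | 43% | 6% |
| 85 | 4% | 35% | 3% |

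**5. Dilution.** If a share b is positive at baseline and stays positive, and a share p of the rest becomes positive, the table shows b + (1 − b)p. Take a true new-onset contrast of 5% against 25%, a ratio of 5.0:

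- b = 10%: 0.10 + 0.90 × 0.05 = 14.5% against 0.10 + 0.90 × 0.25 = 32.5%, a ratio of 2.2.
- b = 20%: 0.20 + 0.80 × 0.05 = 24% against 0.20 + 0.80 × 0.25 = 40%, a ratio of 1.7.

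The risk difference shrinks by the factor 1 − b, from 20 points to 18 and 16. The documents offer nothing from which to estimate an orthostatic rate at baseline, so none is given.

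**The case against.** The strongest reply is that this is one descriptive table among several. The SAP also plans change from baseline in blood pressure by visit and arm, mean plots with confidence intervals, participant listings, and baseline blood pressure by arm. Hypotension and serious hypotension are analysed as treatment-emergent events, with exposure-adjusted rates and Kaplan-Meier estimates. No dose-selection or stopping rule in the documents uses Table 2-4, and the data monitoring committee works from a separate analysis plan. All of that stands and limits the weight of the point. It does not remove it: event analyses depend on what is reported as an adverse event, mean changes do not show individual crossings, and listings give no rate.

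A second reply is that most of the background in the simulation is visit-to-visit noise. At an assumed mean of 82, restricting to baseline-negative participants still flags 17–26% with no drug effect, against 26–36% now. That also stands.

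A third is that the liver and renal rule is not a new-onset rule, since it keeps pre-existing abnormalities that worsen. That is correct, and it bears on the remedy. A new-onset row alone would drop a participant whose diastolic pressure falls from 68 to 50 mmHg on drug.

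Finally, SAP 2.1.1 refers the office baseline derivation to Section 2.12.1, which is not in the published text, so part of the derivation cannot be checked.

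**Conclusion.** The point holds for BP criteria 2, 5, 8 and 11, orthostatic criteria 1–4, and the composites containing them (BP 3, 6, 9, 12, 13; orthostatic 5–7). As written they count any post-baseline occurrence, the entry criteria allow baseline-positive participants, and the footnote supplies no workable exclusion. The expected consequence is a higher background in every arm and a diluted contrast.

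A reader might infer more than the documents support:

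- **That low pressure in general is miscounted.** The entry criteria rule out, or nearly rule out, baseline positivity on the systolic rows.
- **That the table is largely filled with cases unrelated to treatment.** No baseline diastolic distribution or orthostatic rate is given. The assumed range for office diastolic pressure, about 3–25% positive at baseline, runs from trivial to material.
- **That the drug would be shown in a falsely bad light.** Pre-existing cases fall on placebo too.
- **That the trial has no baseline-aware view of hypotension.** The adverse-event and change-from-baseline analyses provide one.

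This is a safety-reporting point. It is worth correcting because hypotension is the main expected risk and the correction is cheap. Alpha, sample size and efficacy inference are unaffected.

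**What to change.** In SAP 2.7.4.2 and Table 2-4, keep the all-participant rows as they are. For the criteria listed in the conclusion, add one of the following, using the randomized-treatment baseline:

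- a shift display from baseline status to worst post-baseline value; or
- a new-onset row with baseline-negative participants as denominator, together with a count of baseline-positive participants who worsened and a stated definition of worsening.

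Reword the footnote to say that its reference to baseline does not apply to absolute cut-offs or to sitting-to-standing drops.

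The data are already planned: SAP 2.3.2 summarises sitting, standing, daytime, night and 24-hour values at baseline. The cost is programming, extra rows, and smaller denominators in the new-onset row. For office diastolic pressure the loss is up to about a quarter under the assumed range (34 × 0.75 ≈ 26 per arm), and more for the composites. The change separates pre-existing from new findings but does not reduce visit-to-visit noise.

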2.10 Patient-reported outcomes

[figure not shown]
Not applicable.

[figure not shown]

Novartis

2.13 Interim analysis

One interim safety analysis will be conducted when approximately first 40 participants complete at least 5 weeks of double-blind treatment. Regular safety data monitoring is planned as specified in Section 4.6 of protocol. No alpha adjustment will be made for the interim safety analysis and safety data monitoring. Interim safety analysis and safety data monitoring will be performed by an independent statistician who will not be involved in the trial conduct. The results will be reviewed by the independent DMC.

The primary analysis will be performed after all participants have completed Week 12 (or discontinued prior to Week 12). A final analysis will be performed after all participants have completed Week 20 (or discontinued prior to Week 20). Formal testing of the primary endpoint with full level alpha of 0.025 (1-sided) will be performed at the primary analysis timepoint.

3 Sample size calculation

3.1 Primary endpoint(s)

The study is planned to randomize 170 participants including approximately 10% lost to follow-up, allocated in the ratio of 1:1:1:1:1 to placebo, XXB750 30 mg SC q4w, 60 mg SC q4w, XXB750 120 mg SC q4w and XXB750 240 mg SC q4w, respectively.

Assuming a common standard deviation of 12 mmHg for mean 24hr SBP change from baseline and a one-sided 2.5% significance level (with adjustments for multiple comparisons using MCP-MOD), a sample size of 150 participants (30 each in placebo, XXB750 30 SC q4w, XXB750 60 mg SC q4W, and XXB750 120 mg SC q4w, and XXB750 240 mg SC q4w) will provide a minimum power of 92% if the underlying true maximum mean 24hr SBP reduction on XXB750 vs placebo is 10 mmHg.

3.2 Secondary endpoint(s)

Assuming a common standard deviation of 12 mmHg for mean 24hr SBP change from baseline and a one-sided 2.5% significance level, a sample size of 30 participants in placebo and in XXB750 highest dose, respectively, will provide approximately 89% power if the true mean 24hr SBP reduction on XXB750 vs placebo is 10 mmHg.

Secondly, same assumption as first secondary endpoint is used for the average change from baseline in mean 24hr SBP at Week 9 and at Week 12 and a one-sided 2.5% significance level, a sample size of 30 participants in placebo and in XXB750 highest dose, respectively, will provide approximately 89% power if the true mean 24hr SBP reduction on XXB750 vs placebo is 10 mmHg.

Lastly, assuming a one-sided 2.5% significance level (with adjustments for multiple comparisons using MCP-MOD), a sample size of 150 participants (30 each in placebo, XXB750 30 mg SC q4w, XXB750 60 mg SC q4W, XXB750 120 mg SC q4w, and in XXB750 240 mg

SC q4w) will provide a minimum power of 76% if the underlying true BP control achievement in placebo and XXB750 doses range from 10% to 45%, respectively.

4 Change to protocol specified analyses

No change from protocol specified analysis was made.

5 Appendix

5.1 Imputation rules

5.1.1 Study drug

The missing or partially missing start or end dates will be handled/imputed using the Novartis AGB global standard approach. Details will be provided in the study PDS document.

5.1.2 AE date imputation

The missing or partially missing AE start or end dates will be handled/imputed using the Novartis ADaM Governance Board (AGB) global standard approach. Details will be provided in the study Programming Datasets Specifications (PDS) document.

5.1.3 Concomitant medication date imputation

The missing or partially missing concomitant medication start or end dates will be handled/imputed using the Novartis AGB global standard approach. Details will be provided in the study PDS document.

5.2 AEs coding/grading

Coding of AE will be done per MedDRA dictionary. The scale of severity grading described in section 8.6.1 of the study protocol will be used.

5.3 Laboratory parameters derivations

Details will be provided in study PDS document.

5.4 Statistical models

5.4.1 Analysis supporting primary objective(s)

Refer to Section 2.5.

5.4.2 Analysis supporting secondary objective(s)

Refer to Section 2.6.

5.5 Rule of exclusion criteria of analysis sets

The following table presents a sample of the rules for participant classification in the analysis sets (Table 5-1).

Table 5-1 Criteria leading to exclusion

Table 5-1	Criteria leading to exclusion
Analysis Set	Criteria that cause
	participants to be excluded
SCR	Not having informed consent;
	Not having disposition page
RIS	Not in SCR;
	Not having disposition page;
	Not receiving single-blind run-in study medication
RAS	Not randomized
FAS	Not in RAS;
	Mistakenly randomized and no double-blind study drug taken
SAF	Not in RAS;
	No double-blind study drug taken

6 References

Agresti A and Caffo B (2000) Simple and Effective Confidence Intervals for Proportions and Differences of Proportions Result From Adding Two Successes and Two Failures. The American Statistician, Vol. 54, No. 4, pp. 280-288.

ICH E9(R1) Harmonized Guideline: addendum on estimands and sensitivity analysis in clinical trials to the guideline on statistical principles for clinical trials. Final version on 20 November 2019.

